## 2. INTRODUCTION

This document details the proposed presentation and analyses for the main analysis reporting results from the USAID and Clearly funded randomised controlled trial PROSPER II (PROductivity Study of Presbyopia Elimination among aRtisans: a randomised trial on the effect of providing near glasses on the productivity of Indian textile workers). The results reported in this publication will follow the strategy set out here. Subsequent analyses of a more exploratory nature will not be bound by this strategy, although they are expected to follow the broad principles described. The principles are not intended to curtail exploratory analysis (for example, to decide cut- points for categorisation of continuous variables), nor to prohibit accepted practices (for example, data transformation prior to analysis), but they are intended to establish the rules that will be followed, as closely as possible, when analysing and reporting the trial.

The analysis plan will be available on request when the principal manuscripts are submitted for publication. Suggestions for subsequent analyses by journal editors or referees will be considered carefully and carried out, as far as possible, in line with the principles of this analysis plan.

Any deviations from the statistical analysis plan will be described and the rationale given in the final report of the trial. The analysis will be carried out by an identified, appropriately qualified and experienced statistician, who will ensure the integrity of the data during processing. Examples of such procedures include quality control and evaluation procedures.

### **Trial Statisticians**

**[name], Stellenbosch University, SA**

## 4. BACKGROUND INFORMATION

### 4.1 Rationale

PROSPER II is a randomised controlled trial (RCT) assessing the effect of reading glasses on the productivity of presbyopic textile workers in Karnataka, India.

### 4.2 Objectives of the trial

Globally, 2.7 billion people do not have the eyeglasses they need to earn, learn, travel safely in traffic and participate in civic life. Among these, 1.1 billion people lack a simple pair of reading glasses to correct impaired near vision, called presbyopia. Presbyopia, the essentially universal decline in unaided near vision that occurs with aging, is the world's most common cause of vision impairment. Loss of accommodation (ability to change focus from distance to near) due to presbyopia can begin as early as age 30 years, commonly becomes functionally apparent by 40, and is essentially complete by 55, meaning that presbyopia is most common at the height of the working years. Few trials have been published which address the question of whether healthcare interventions can improve work performance as well as workplace retention, especially among persons over the age of 40 in low and middle-income countries (LMICs). We propose to carry out a randomized trial measuring the effect of presbyopic correction on productivity in Indian textile workers in the Karnataka area.

PROSPER II will assess the impact of free reading glasses on productivity for workers in textile factories in Karnataka, India. We hypothesise that the change in worker efficiency over the 3-month evaluation period will be greater in the Intervention compared to the Control group, adjusting for baseline efficiency.

### 4.3 Trial design

PROSPER II is an investigator-masked, multi-center randomized controlled trial.

### 4.4 Eligibility

#### 4.4.1 Inclusion criteria

Shahi employees will be eligible to participate if:

- they are aged 35 years or older
- they have presbyopia, defined as an unaided near visual acuity of N6.3 or worse in both eyes.
- have worked in the production department as tailors or Kajbutton operators for 6 weeks or more
- they require a new pair of glasses to improve their near vision.
- they have a corrected near visual acuity of N4 or better in both eyes.

#### 4.4.2 Exclusion criteria

Shahi employees will be ineligible to participate if:

- have ocular pathology in either eye detected during the eye examination, or history of such disease based on self-report
- have a low likelihood of completing follow-up in the study due to current plans to move out of the area or leave employment at Shahi during the follow-up period

#### 4.5 Interventions

Eligible participants will be randomly assigned to Intervention and Control Groups (1:1). Intervention group participants will receive free reading glasses within a month of undergoing a vision screening at the factory. Control group participants will receive reading glasses at the end of the assessment period (four months after vision screening). The trial will be investigator-masked, but not participant-masked, because the investigators do not feel provision of zero-power glasses to the control group is ethical. However, participants will have limited knowledge of the study hypothesis, limiting potential placebo effects.

#### 4.6 Definition of primary and secondary outcomes

##### 4.6.1 Primary outcome

The primary outcome for sew-ers enrolled in the study is efficiency, defined as the number of items completed divided by target number of items per unit time (as defined by Shahi factory standards). Daily mean efficiency for each participant will be assessed from trial entry to closure as recorded by a productivity measurement system executed by the GBL team using a PushButton counter device.

##### 4.6.2 Secondary outcomes

The secondary outcomes are:

- changes in skill grade and associated change in wage
- adherence with spectacle wear
- change in attitude towards eye health, glasses wear and uptake of eyecare services
- Visual Function using the APEDS Visual Function Questionnaire
- intervention cost-benefit analysis

#### 4.7 Hypothesis framework

PROSPER II is a superiority trial comparing glasses wear to non-wear. Analysis of the trial will entail calculation of treatment effect measures and confidence intervals to assess the difference between the two arms. Results from the statistical analysis will generally be presented by two-sided confidence intervals (CIs) with a confidence level of 95%. Superiority will be claimed if the two-sided p-value is less than 5% and the treatment estimate favours the use of glasses. If the lower limit is above 0, superiority of glasses-wear against non-wear can be concluded.

#### 4.8 Sample size & power

The primary outcome is efficiency, defined as the number of items completed divided by target number of items per unit time as defined by industry standards. Efficiency is thus a

dimensionless ratio. We will top code the efficiency at 99th percentile to account for outliers. This outcome will be compared between the two study groups. An increase in mean efficiency of 0.0425 in the intervention group compared to the control group (the latter having a baseline mean of 0.53 per day and SD 0.19, based on Shahi records) is deemed economically meaningful to Shahi. Effects of this size have been detectable in other trials in this setting. With a two-sided significance level of  $p=0.05$ , power of 90% and a serial correlation in outcomes of 0.8 (data from previous Shahi trials), our sample size calculation yields a required sample size of 152 subjects per group. Allowing for 80% adherence and 10% loss to follow-up each month, we calculated that a sample size of 500 individuals (250 per group) is required.

#### **4.9 Intervention allocation**

Consenting participants eligible for the trial will be divided into eight strata according to age (<median,  $\geq$ median), work tenure at the textile factory (<median,  $\geq$ median), efficiency during baseline assessment (<median,  $\geq$ median). Participants in each stratum will be randomized 1:1 with block size of four to either the Intervention or Control Groups. The randomisation sequence will be generated by the researchers at GBL using the statistical software package Stata, and concealed until a worker is determined eligible and has agreed to participate. The field team will have a list provided by the textile factories of potential participants, their current age, tenure and baseline productivity. Study personnel will access the random assignment for each participant according to the correct age-tenure-productivity stratum only at the time of enrolment.

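### A single fixed block size of four in a participant-unmasked trial makes up to an expected one third of allocations deducible by a fully informed observer; varying and withholding the block size is a cheap improvement

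*SAP*

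**What the plan says.** SAP section 4.9 defines the strata by splitting age, work tenure and baseline efficiency at their medians: "Consenting participants eligible for the trial will be divided into eight strata according to age", followed by the other two variables. Within strata, "Participants in each stratum will be randomized 1:1 with block size of four". Section 4.9 of the combined protocol and SAP has the same block rule.

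On concealment, the SAP says that the sequence is "concealed until a worker is determined eligible and has agreed to participate", and that study personnel look up the assignment for the relevant stratum "only at the time of enrolment". It names no custodian for the list and no mechanism of concealment. On the sequence itself: "The randomisation sequence will be generated by the researchers at GBL using the statistical software package Stata". GBL staff also collect baseline efficiency, daily efficiency and adherence (SAP sections 4.10.1, 4.10.2 and 6). The combined document instead assigns the sequence to a study statistician at an outside clinical trials unit.

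On what staff know: "The field team will have a list provided by the textile factories of potential participants, their current age, tenure and baseline productivity". On masking (SAP section 4.5): "The trial will be investigator-masked, but not participant-masked".

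**The concern.** Hiding a list protects only those entries that cannot be worked out from what has already been revealed. With every block the same small size, the last entry of a block follows from the first three, and sometimes the third follows from the first two. Here the field team can place the next worker in a stratum before enrolment. Whoever looks up assignments can keep a tally, and unmasked participants make earlier assignments visible in time on the factory floor.

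Foreknowledge could act in the consent conversation, or through the exclusion of workers who "have a low likelihood of completing follow-up in the study". If enrolment depended on the predicted arm, the groups could differ in unmeasured traits such as motivation or intention to stay. The planned covariate adjustment reaches only what is measured.

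**Working it through.** The documents give no figure for predictability, so there is none to reproduce.

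**Inputs.** Block of four, 1:1, eight strata (SAP 4.9); total sample 500 (SAP 4.8). Assumptions: strata of equal size, 500/8 = 62.5 workers each; workers enrolled one at a time; an observer who knows the block size and sees every earlier assignment in the stratum.

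**Allocations known with certainty.** There are 6 equally likely orderings of two Intervention and two Control entries. An entry is certain when only one arm remains in the block.

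| Position in block | Probability of certainty | Probability that best guess is right |
|---|---|---|
| 1 | 0 | 1/2 |
| 2 | 0 | 2/3 |
| 3 | 1/3 | 2/3 |
| 4 | 1 | 1 |

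- Certain share: (0 + 0 + 1/3 + 1)/4 = 1/3. That is 500/3 ≈ 167 of 500, or 62.5/3 ≈ 21 per stratum.
- Best-guess accuracy: (1/2 + 2/3 + 2/3 + 1)/4 = 70.8%, against 50% by chance.

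**Several sites sharing one stratum list.** The trial is multi-centre (SAP 4.3), factory is not a stratum, and the number of sites is not given. Assume that each entry goes at random to one of k sites, and that staff know the position in the block but see only their own site's assignments. Certainty then requires that both entries of one arm came earlier at the same site:

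- Position 3: (1/3)(1/k²). Position 4: 1/k². Share: (1/3 + 1)/(4k²) = 1/(3k²).
- k = 2: 1/12 = 8.3%. k = 3: 1/27 = 3.7%. k = 4: 1/48 = 2.1%. Simulation gives the same values.
- If each site has its own list, the one-third figure can still apply.

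**Varied block sizes.** Simulation with 63 workers per stratum; the observer knows the set of sizes but not their order, and updates after each assignment.

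| Block sizes | Certain | Best guess right |
|---|---|---|
| Fixed 4 | 32.2% | 70.4% |
| 4 and 6 at random | 5.5% | 68.9% |
| 4, 6 and 8 at random | 2.2% | 67.6% |

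The fixed-4 row is slightly below 33.3% and 70.8% because the last block in a stratum of 63 is incomplete. Like for like, the excess over chance guessing falls from 20.4 to 17.6 percentage points, a cut of about 14%. Varying the sizes removes nearly all certainty but little of the better-than-chance guessing.

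**Balance.** A block of 8 can leave a stratum unbalanced by at most 4, a block of 4 by at most 2. With one list per stratum, the worst case over eight strata is 32 against 16. At 266 against 234 workers, efficiency relative to 250 per group is 266 × 234/250² = 0.996.

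**The case against.** **The block size may not have been known.** A reader might infer that it was published while workers were being enrolled. The documents do not support this: the introduction of each makes the plan available on request when the principal manuscripts are submitted. Neither says that field staff are told the block size. This objection stands, so one third is a ceiling and not a description of what staff knew.

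**Enrolment may have been complete before assignment.** Medians need an assembled cohort or preset cut-points, and SAP section 4.10.1 collects four weeks of baseline efficiency for enrolled workers before randomisation. If consent and eligibility were all settled before any assignment was revealed, predictability could not affect who enters. However, section 4.9 also has each assignment accessed at enrolment. The text supports both readings and settles neither.

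**Tracking is harder than it looks.** Staff at one site may not see assignments elsewhere. Glasses are a delayed signal, since SAP section 4.5 allows up to a month after screening. Both points reduce the risk, although those who look up assignments need not wait for the glasses.

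**The exclusion criterion is narrower than its opening words.** It is tied to a worker's current plans to move away or leave the employer, so it is not a free judgement by staff. This stands. The consent conversation remains as a route.

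**The analysis adjusts for much of the outcome variation.** Baseline efficiency is in the primary model, and the assumed serial correlation of 0.8 implies that it explains about 0.8² = 64% of outcome variance. A reader might infer that the treatment effect will be biased by a material amount; no calculation here shows that.

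**Conclusion.** The concern holds in a limited form. A fixed block of four gives a fully informed observer certainty about an expected one third of allocations, at most about 167 of 500, and a 71% success rate by best guess. That result requires knowledge of the block size, sight of every earlier assignment in the stratum, and one-by-one enrolment. Under the shared-list assumption the certain share is about 8% with two sites and about 2% with four. It is irrelevant to enrolment if all workers entered before any assignment was revealed.

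The documents do not establish that staff had the necessary knowledge, and they do not state any safeguard that would make the design harmless. The stated concealment does not cover entries that can be deduced. This is therefore a cheap improvement to a stated rule, not evidence of a compromised trial.

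**What to change.** If randomisation has not taken place:

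- Draw block sizes at random from 4, 6 and 8 within each stratum.
- Keep the sizes out of every document that the field team sees, and hold them only in the randomisation file.
- State in SAP section 4.9 who holds that file, and whether assignments are released one by one or only after all workers are enrolled.

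If randomisation is complete, report the fixed block size, who held the list, and whether enrolment preceded all assignments.

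The cost is one line of the randomisation program and a few sentences in the SAP. The price in balance is a possible difference of up to 4 instead of 2 per stratum. The adjustment for age, tenure and baseline efficiency already planned in SAP section 9.1 covers this. The change should not be presented as removing predictability altogether, since best-guess accuracy stays near 68%.

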#### **4.10 Data collection schedule**

##### **4.10.1 Data collection before trial**

Demographic data will be collected through Shahi's Human Resource database and clinical information will be collected using VisionSpring's Eye Examination Form (Annexe 1). Baseline efficiency data for enrolled workers will be collected by GBL enumerators for a 4-week baseline period prior to randomization.

##### **4.10.2 Data collection during trial**

Daily efficiency data for each employee in the sewing department will be collected routinely by a productivity measurement system executed by the GBL team using a PushButton counter device. Wage and employment status data will be collected on a monthly basis from Shahi's Human Resource division. These data will be assessed at the end of the 3-month intervention period. Intervention costs will be collected by VisionSpring and assessed at the end of the 3-month intervention period. Secondary outcome data will be collected using the following data collection forms

- Baseline Assessment (following eye examination)
- Endline Assessment (at the end of the 3-month intervention period)
- Spectacle Wear Compliance (on a weekly basis over the 3-month intervention period)

#### **4.11 Interim analyses and stopping rules**

Given the low risk to subjects and the relatively short duration of the trial no interim analyses will be conducted. An independent Data Monitoring Committee (DMC) will not be established for PROSPER II.

#### **4.12 Trial reporting**

The trial will be reported according to the principles of the CONSORT statement.

### **5. PROTOCOL DEVIATIONS**

A protocol deviation is defined as a failure to adhere to the protocol such as the wrong intervention being administered, incorrect data being collected and documented, errors in applying inclusion/exclusion criteria or missed follow-up visits due to error.

#### **5.1 Major**

The following will be defined as major protocol deviations:

- Enrolled workers have not provided Informed Consent
- Data considered fraudulent

#### **5.2 Minor**

The following will be defined as minor protocol deviations:

##### **5.2.1 Participants randomised in error**

- Employees <=35 years, or employed <6 weeks, or not employed in the production department as tailors or Kajbutton operators assigned to Intervention Group

##### **5.2.2 Participants who do not receive allocated intervention**

- Workers in the Intervention Group not receiving glasses
- Workers in the Control Group received glasses from VisionSpring (workers in the Control Group deciding to purchase glasses from an external eyecare service provider during the course of the study will not be considered a protocol deviation, and their data will be analysed under Intention To Treat)

### **6. ADHERENCE TO THE INTERVENTION**

Adherence to the intervention will be assessed through observation of spectacle wear while working. Adherence will be measured surreptitiously on a daily basis. The enumerators assessing spectacle wear compliance are GBL staff members familiar to Shahi workers but are not revealed to be collecting glasses wear adherence data to ensure minimum modification of compliance behaviour in present of enumerators.

### **7. ANALYSIS POPULATIONS**

## 7.1 Primary analysis strategy

All outcomes will be assessed by Intention To Treat: participants will be analysed in the groups into which they were randomly allocated, i.e. comparing the outcomes of all workers allocated to the Intervention Group with workers allocated to the Control Group, regardless of allocation received.

## 7.2 Descriptive analysis population

Baseline demographic and clinical characteristics will be reported for all workers randomised for whom we have data available, excluding protocol deviations randomised in error where Informed Consent has not been obtained.

# 8. DESCRIPTIVE ANALYSES

## 8.1 Representativeness of trial population and participant throughput

The flow of participants through each stage of the trial will be summarised using a CONSORT diagram (see below). We will report the numbers of participants:

[figure not shown]
- at participating sites
- eligible for eye examination
- examined
- stratified and randomly assigned
- received intended intervention
- withdrawals
- randomised in error
- included in the analysis

## 8.2 Baseline comparability of randomised groups

Participants in randomised groups will be described separately with respect to the following characteristics at trial entry:

- age
- sex
- education level
- marital status
- number of children and dependants
- median wage compared to urban Bangalore and urban India
- visual function (APEDS VFQ tool)
- uncorrected visual acuity in each eye separately at distance and both eyes together at near
- mean power of near correction required
- baseline work productivity
- attitudes towards vision correction
- access to local eyecare services
- history of uptake of eyecare services

## CONSORT Flow Diagram

Numbers (with percentages) for binary and categorical variables and means (and standard deviations), or medians (with lower and upper quartiles) for continuous variables will be presented; there will be no tests of statistical significance performed nor confidence intervals calculated for differences between randomised groups on any baseline variable.

### 8.3 Losses to follow-up

Missing data due to loss to follow-up is likely to be linked to staff turnover. Worker turnover at Shahi is accounted for in the sample size calculation and, based on historical data, is not expected to exceed 10% per month.

### 8.4 Adherence to intervention

The percentage of glasses wear adherence per week will be reported for the duration of the trial.

## 9. COMPARATIVE ANALYSES

### 9.1 Analysis of primary and secondary outcomes

The primary endpoint is difference in efficiency during the 3 months of intervention between the treatment and control groups. The objective is to show that glasses-wear is superior to non-wear in improving worker efficiency. The null-hypothesis will be rejected on a 5% level if the two-sided 95% CI of the treatment full analysis set difference  $\mu_{\text{glasses}} - \mu_{\text{non-glasses}}$  excludes 0. If the lower limit is above 0, superiority of glasses wear against non-wear can be concluded. The hypothesis will be tested using an analysis of covariance (ANCOVA) model. In the regression specification, the outcome variable will be daily mean efficiency for each participant per day. The factors, covariates and interaction terms in the ANCOVA model are listed in the table below.

Factors and covariates at baseline	Type	Categories
Randomised treatment	Factors	Intervention, Control
Sex	Factors	Male, Female
Skill grade	Factors	<median, $\geq$ median
Factory type	Factors	Urban, rural
Spectacle wear compliance	Factors	<median, $\geq$ median
Age	Covariate	Not applicable
Baseline efficiency	Covariate	Not applicable

The factors and covariates will be included in the model as main effects in an additive structure. The estimated treatment difference between glasses-wear and non-wear will be reported together with the associated two-sided 95% CI and corresponding p-value. The standard errors will be clustered at the individual participant level.

Linear regression analyses will be performed on potential determinants of primary and secondary outcomes. The study group and all significant variables with p values less than 0.20 in simple regression analyses will be included in multiple regression models. Histograms, normal quantile plots (QQ Plot), and the Shapiro-Wilk normality test will be used to test the normality assumption in regression models. For the APEDS VFQ tool, a composite score (16 items) will be created on 0-100 scales, with higher scores indicating better results. Intervention costs will comprise the screening test, glasses (and any replacement thereof) as well as direct and indirect costs to the company for facilitating workplace-based sight tests. We will report cost effectiveness distinguishing between study costs and program costs. The cost effectiveness analysis will include both the costs to identify presbyopia and treat presbyopia.

The analysis of primary and secondary outcomes will be adjusted for the minimisation factors (age, work tenure at the textile factory, efficiency during baseline assessment) to account for the correlation between treatment groups introduced by balancing the randomisation. The analysis will incorporate adjustment for glasses wear adherence to

account for any potential confounding effect on the productivity measures. Adherence to wearing glasses will be considered a covariate in the regression models assessing primary and secondary outcomes. Both the crude unadjusted and adjusted estimates will be presented, but the primary inference will be based on the adjusted analysis.

For multiple imputation of missing data in assessing primary outcomes we will create 20 copies of the data, in which missing values shall be imputed by chained equations, and the datasets will be averaged.

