#### **4.4.2 Exclusion criteria**

Shahi employees will be ineligible to participate if:

- they own reading or distance glasses (regardless of accuracy)
- have ocular pathology in either eye detected during the eye examination, or history of such disease based on self-report
- have a low likelihood of completing follow-up in the study due to current plans to move out of the area or leave employment at Shahi during the follow-up period

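### The decision rule concludes that glasses wear beats non-wear, but what is randomised is early against deferred provision of free near glasses

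*SAP*

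**What the plan says.** **The claim.** SAP 4.7 states: "PROSPER II is a superiority trial comparing glasses wear to non-wear". It adds: "Superiority will be claimed if the two-sided p-value is less than 5% and the treatment estimate favours the use of glasses". SAP 9.1 writes the parameter as a glasses mean minus a non-glasses mean and ends: "If the lower limit is above 0, superiority of glasses wear against non-wear can be concluded".

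**The design.** SAP 4.5 randomises 1:1 to free glasses within a month of screening, or to glasses after the assessment period, four months from screening. SAP 7.1 analyses all outcomes by intention to treat. SAP 4.2 gives the aim as provision: "PROSPER II will assess the impact of free reading glasses on productivity for workers in textile factories in Karnataka, India".

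**Who may wear glasses.** Under SAP 5.2.2, a control worker "deciding to purchase glasses from an external eyecare service provider during the course of the study will not be considered a protocol deviation", and that worker stays in the intention-to-treat comparison. SAP 4.4.1 requires that "they require a new pair of glasses to improve their near vision", and SAP 4.4.2 has no ownership criterion. The Combined protocol and SAP (version 1.0), section 4.4.2, does exclude workers if "they own reading or distance glasses (regardless of accuracy"). Its sections 4.7 and 9.1 carry the same wear wording. SAP 4.8 allows for 80% adherence and names no allowance for wear among controls.

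**The deciding model.** The covariate table in SAP 9.1 includes spectacle wear compliance. The text of 9.1 makes adherence a covariate and rests the primary inference on the adjusted analysis.

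**The concern.** The SAP names two different quantities. The aim, the allocation and the analysis population all concern giving workers free glasses sooner rather than later. The hypothesis, the parameter and the permitted conclusion concern wearing glasses against not wearing them. The two coincide only if everyone in the intervention arm wears glasses and nobody in the control arm does, and the SAP plans for neither.

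This affects how either result is read. A positive result would be reported as the effect of wear, with a magnitude that belongs to provision, and the cost-effectiveness report in 9.1 depends on which of the two is meant. A null result could be taken to mean that wear does not help, when the arms may simply have differed too little in wear.

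The adjustment for wear makes the mismatch worse. The estimate on which the primary inference rests is neither the effect of provision nor the effect of wear.

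**Working it through.** **Inputs from SAP 4.8.** Difference 0.0425, SD 0.19, two-sided 5%, "power of 90% and a serial correlation in outcomes of 0.8", 152 per group before inflation, 80% adherence, 10% loss per month, 250 per group enrolled.

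**Step 1: reproduce the plan's figure.** n per group = 2 × [SD × (1.960 + 1.282) / difference]² × (1 − ρ²) = 420.0 × (1 − 0.64) = 151.2, rounded up to 152. This matches.

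**Step 2: what the crude comparison by allocation estimates.** Assume that:
- glasses act only through wear;
- the effect of wear is 0.0425;
- 80% of the intervention arm wears glasses;
- a share q of controls wears adequate correction.

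The crude difference is then 0.0425 × (0.8 − q). Power = Φ(difference / SE − 1.96), with SE = 0.19 × √0.36 × √(2/n) = 0.114 × √(2/n). The documents give no q, so the rows below are illustrations.

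| q (assumed) | 0.8 − q | Crude difference | Power, n = 250 | Power, n = 182 |
|---|---|---|---|---|
| 0 | 0.8 | 0.0340 | 91.5% | 81.2% |
| 10% | 0.7 | 0.0298 | 83.1% | 70.2% |
| 20% | 0.6 | 0.0255 | 70.6% | 57.0% |
| 30% | 0.5 | 0.0213 | 54.9% | 42.8% |

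Here 182 is 250 × 0.9³. That column is pessimistic, because leavers contribute data until they leave.

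**Step 3: what the deciding model estimates.** Under the same assumptions the expected outcome, given allocation and wear, is a constant plus 0.0425 × wear. Once wear is in the model, the coefficient on allocation is zero whatever q is. A simulation (2,000 runs, 182 per arm, each worker's own wear entered in both arms) agrees:

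| q (assumed) | Crude difference | Wear-adjusted treatment coefficient | Rejection rate, adjusted |
|---|---|---|---|
| 0 | 0.0340 | −0.0001 | 5.5% |
| 10% | 0.0297 | −0.0003 | 5.2% |
| 20% | 0.0258 | 0.0005 | 4.8% |
| 30% | 0.0211 | 0.0001 | 4.5% |

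A real benefit of wear would then be detected at roughly the nominal 5% rate. The SAP does not say how wear is coded for controls, so this shows the mechanism and does not predict the trial's estimate.

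**The case against.** **The operative text is already by arm.** The endpoint in 9.1 compares the treatment and control groups, the model factor is randomised treatment, and 80% adherence is already allowed for. All true. It makes the correction cheap, but 4.7 and 9.1 still state a conclusion about wear.

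**A positive crude result is conservative.** If allocation acts only through wear and never reduces it, a crude lower limit above 0 does imply a benefit of wear among those whose wear changed. This stands. A reader might infer that the rule produces false claims of superiority, but dilution does not do that. The fault is in the label and the size attached to it.

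**The dilution may be small.** Every participant must need a new pair, so an owner's existing pair is inadequate and should not be credited with the full gain. Its effect is also partly reflected in baseline efficiency, which is a covariate. This stands too. Only controls with adequate correction count towards q.

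**Wear is measured.** SAP section 6 has wear observed daily at work, 4.6.2 lists it as a secondary outcome, and 8.4 reports it weekly. A reader might infer that the report could not show how far the arms differ in wear, but the documents do not support that. What they leave open is whether a control's own glasses are recorded and whether wear is reported by arm. Current ownership or use is absent from the 8.2 list, but the baseline forms are not reproduced and may capture it.

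**Conclusion.** The mismatch between the randomised contrast and the stated conclusion is real and should be corrected. A lower limit above 0 from a comparison by allocation supports superiority of early over deferred provision. It does not give the size of the effect of wear, and a null result does not show that wear fails to help.

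The size is unknown. On the assumptions in step 2, the crude difference is 80% of the effect of wear at q = 0 and 60% at q = 20%, that is, 0.034 and 0.026 if the effect of wear is 0.0425.

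Two stronger readings are tempting and are not supported:
- **That the effect of wear is understated.** This is only the expected direction for the crude estimate, if glasses act solely through wear. SAP 4.5 leaves participants unmasked, which could push the other way. Any stated percentage loss depends on an assumed q: for example 0.1/0.8 = 12.5% at 10%, or 0.3/0.8 = 37.5% at 30%.
- **That rewording alone is enough because the primary analysis is plain intention to treat.** It is not. The deciding model adjusts for wear observed after randomisation, so it would not estimate the effect of provision even under corrected wording.

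**What to change.** 1. In SAP 4.7 and 9.1, define the two means by allocated arm. State the conclusion as superiority of early (within a month of screening) over deferred provision of free near glasses.
2. Remove spectacle wear compliance and adherence from the primary model (the 9.1 table and the paragraph on adherence adjustment). Adjust only for baseline variables. Without this, item 1 names a quantity that the model does not estimate.
3. State that the existing wear observation records any near glasses in both arms, and report it by arm. Add current near-glasses ownership or use to the 8.2 list if the baseline forms do not already capture it. A subgroup by ownership is optional.
4. Report any effect of wear only as a supportive instrumental-variable (two-stage least squares) estimate with allocation as the instrument. State its assumptions: allocation acts only through wear, which is open to doubt without participant masking, and never reduces it. State also that an inadequate old pair is not equivalent to a correct new one.

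The cost is revised wording, possibly one baseline question, one supportive model and a narrower headline claim. Wear observation is already planned.
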